## **List of Abbreviations**

PREVENT	Prehabilitation of Veterans with Exercise and Nutrition
RR&D	Rehabilitation Research and Development Service
KDIGO	Kidney Disease Improving Global Outcomes
GFR	Glomerular Filtration Rate
PAEC	Pre-Anesthesia Evaluation Clinic
POSH	Preoperative Optimization of Senior Health (Clinic)
5RSTS	Five Repetition Sit-to-Stand
TMST	Treadmill Stress Testing
MoCA	Montreal Cognitive Assessment
ASA	American Society of Anesthesiologists
VCM	Virtual Care Management
RPE	Rate of Perceived Exertion

## **1.0 Purpose**

The goal of VA's RR&D office is to maximize functional recovery. Considering that goal, our proposal allows us to test an intervention that combines the fundamentals of Physical Medicine and Rehabilitation with state-of-the-art nutritional support and innovations in care such as telehealth to optimize patients before high-risk surgery. This intervention has the potential not only to reduce complications and hospital readmissions, but also to maximize functional recovery and quality of life for thousands of veterans undergoing high-risk surgery every year. Furthermore, the proposal is the first step in the design and implementation of prehabilitative services for veterans living in rural areas and those with inadequate support or transportation.

## **2.0 Background and Significance**

Approximately half a million operations are performed each year in VA hospitals across the country. Veterans undergoing high-risk surgery have a 1 in 5 chance of suffering complications, a 1 in 10 chance of being readmitted to the hospital within 30 days, and a 1 in 50 chance of dying within 30 days. Long-term survival is significantly reduced for those patients who have perioperative complications, even if they survive to leave the hospital.

Low fitness and poor functional status are among the strongest predictors of postsurgical complications. Prehabilitation takes advantage of the weeks leading up to surgery in order to improve fitness, mobility and nutrition in preparation for the upcoming surgical stress. Indeed, prehabilitation has been shown to improve fitness, reduce complications, and improve quality of life in high-risk surgical patients. The most effective prehabilitation programs combine exercise with nutritional support (are multimodal). They provide exercise that is supervised and individualized and ensure that exercise intensity is appropriate and escalated according to improvements in fitness and strength. Most supervised prehabilitation programs are facility-based, with participation limited by travel time, distance, and transportation. Unfortunately, home-based prehabilitation programs have shown small effect sizes and low compliance rates, likely because the intensity required in programs of such short duration is often not achieved with such unsupervised programs.

The goal of prehabilitation is to enhance fitness and physical function in anticipation of a forthcoming physiological stress. One of the main components of prehabilitation is a structured exercise protocol that typically includes aerobic and resistance exercise. By repeatedly exposing the body to physiologic stress, physical activity stimulates muscle protein synthesis resulting in improved objective markers of physical fitness and improved strength. Nutrition is another key component of prehabilitation because it works synergistically with exercise. It is generally accepted that exercise provides the primary anabolic stimulus and nutrition potentiates the muscle protein response. Indeed, studies using stable isotopes have shown that exercise without provision of adequate protein does not result in optimal gains in muscle accretion. After a single session of resistance exercise in healthy individuals, muscle protein breakdown and synthesis are both stimulated. Net protein balance in the muscle (protein synthesis minus breakdown) remains negative after exercise until exogenous amino acids are administered. Amino acids stimulate both the synthesis of structural (myofibrillar) muscle protein as well as the synthesis of mitochondrial proteins, required for aerobic metabolism and maintenance of functional exercise capacity.

Compliance with prehabilitation programs is extremely variable, with reported rates that vary between 16 and 100%. Hospital-based prehabilitation programs delivered under direct

supervision have the highest compliance rates, yet barriers such as travel time, distance, and transportation limit participation. Previously, we found that rural veterans lack access to exercise programs. Home-based interventions are attractive but are typically unsupervised and associated with reduced compliance rates. If applied to prehabilitation, new telehealth technologies could address the shortcomings of home-based approaches because they combine accessibility with supervision, encouraging compliance while ensuring adequate training intensity. However, this mode of prehabilitation care delivery has not yet been studied in a veteran population.

The proposed “tele-supervised” exercise program may allow Veterans living in rural areas and lack transportation or are otherwise unable to travel to participate in prehabilitation in preparation for an upcoming high-risk operation. These findings are expected to inform the design of a larger multicenter trial on the effects of multimodal prehabilitation on surgical outcomes and healthcare resource utilization and to foster the widespread adoption of multimodal prehabilitation in preoperative optimization of high-risk patients at the Durham VAHCS and other VA Health Care Systems. It represents an important step towards providing optimal perioperative care for veterans by identifying and improving fitness, physical function, and nutrition before surgery in a manner that is not geographically constrained. These improvements will contribute to the reduction in health care costs due to decreased complications and fewer readmissions following surgery in high-risk patients.

### **3.0 Design**

The objective of this protocol is to determine the feasibility, acceptability, and safety and estimate the effect size of a multimodal prehabilitation program that incorporates exercise training and nutritional support. The central hypothesis is that a short-duration, individualized multimodal prehabilitation intervention administered prior to high-risk surgery is feasible and safe at a tertiary VA hospital. The intervention will consist of individualized exercise training delivered remotely using VA telehealth technology, combined with nutritional support consisting of tailored nutritional advice, protein supplementation, and multivitamin and vitamin D supplements. Based on local surgical volume, local expertise in the Gerofit and telehealth exercise programs in non-surgical populations, and published participation numbers and attrition rates, we anticipate that 24 patients can be enrolled and safely participate in a home-based telehealth exercise program plus nutritional support. Adherence to the intervention will be encouraged by use of automated text messages.

This is a pilot intervention that combines the most promising elements of prehabilitation along with innovations in telehealth delivery to develop a VA patient-centered multimodal prehabilitation program with the following specific aims:

- To determine the feasibility, acceptability, and safety of a short-term (3-4 week) multimodal prehabilitation intervention followed by a 4-6 week period of rehabilitation in a cohort of veterans undergoing high-risk surgery.
- To estimate the effect size of a multimodal prehabilitation program for important postoperative outcomes (improvements in functional capacity and physical function, anxiety/depression, and quality of life).

While aspects of the intervention are novel and the work exploratory, based on available evidence, we expect the Cohen’s effect sizes for functional capacity and quality of life to be approximately 1.6 and 0.4, respectively.

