## **5.0 Selection of Subjects**

## **5.1 Study Population**

The study population includes frail veterans scheduled to undergo high-risk surgical procedures. Veterans scheduled for surgery are evaluated in either the Pre-Anesthesia Evaluation Clinic (PAEC) or the Preoperative Optimization of Senior Health (POSH) Clinic. We plan to screen veterans who are seen in either clinic and enroll a total of 24 patients over 2 years.

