### 8.2 Study Procedures

Eligible veterans who consent will enroll in a program of individualized exercise training combined with nutritional support during intervening time before and after surgery.

Study procedures and assessments are outlined in Figure 1 below.

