### **8.2.3 Assessments and Supplemental Interventions**

Objective physical function assessments will be performed at baseline (T1), before surgery (T2), immediately prior to hospital discharge (T3), and then again 6 weeks postoperatively (T4) by administering the **2MST,5RSTS and HGS tests** either in-person or remotely using telehealth technology (see Table 1 for details).

The nutritional support intervention will be assessed at baseline (T1), before surgery (T2), immediately prior to hospital discharge (T3) and then again 6 weeks postoperatively (T4) using **anthropometrics**, a weekly **24-hour dietary recall** (via telephone or videoconference, see Appendix 6), and the administration of the **PG-GSA**, a validated nutritional assessment instrument (see Table 1 for details).

Both the exercise and nutritional support programs will be supplemented with **text messages** on veterans who own text message-enabled cellphones.

Messages will be sent daily using the VA Annie App during the prehabilitation period (T1 - T2). The purpose of these messages is as a reminder about the timing of training sessions, to prompt independent exercise on days between formal sessions, to take protein supplement following exercise, and to maintain a nutritional diary (see above).

Text messages and weekly telephone or videoconference calls will resume upon hospital discharge and extend until the 6-week follow-up visit (T4).

Anxiety, depression, and health-related quality of life will be assessed using the HADS and SF-36 questionnaires at baseline (T1), before surgery (T2), immediately prior to hospital discharge (T3), and 6 and 24 weeks postoperatively (T4 and T5, respectively). These questionnaires will be administered either in person or via telephone or videoconference.

Details and timelines for each of these assessment instruments are described in Table 1.

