## **13.0 Data Analysis and Statistical Considerations**

Feasibility will be assessed by calculating the acceptance rate, measured as the number of patients enrolled divided by the number eligible. In addition, we will evaluate veterans' reasons for enrollment or non-enrollment in the program using patient interviews and semi-structured questionnaire (see Appendix 4). No PHI will be recorded in questionnaires obtained from eligible but non-recruited veterans.

Acceptability will be measured by rate of compliance with the exercise/nutrition programs. For the exercise intervention, the percentage of patients completing  $\geq 75\%$  of sessions divided by the number of enrolled patients will be calculated. For the nutritional intervention, compliance will be measured by the percentage of patients with  $\geq 75\%$  adherence to protein intake goal, as assessed using the text message-based nutrition diary, lids returned, and 24-hour recall administered during the weekly telephone call.

Safety will be evaluated by the number of adverse events (significant injury or medical event) during exercise. A significant injury or medical event is defined as an event that causes the participant to seek attention from a health professional or limits their activities of daily living for at least two days.

Effect size will be estimated by comparing physical function before and after the prehabilitation intervention, as measured by the 5RSTS and the 2-minute step tests using Cohen's D. Changes in health-related quality of life (SF-36) and anxiety and depression (HADS) before surgery and at the 6-week and 24-week study periods following surgery will be calculated.

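### Aim 2 promises the program's effect size for postoperative outcomes, but the planned single-arm before-after d is an uncontrolled, preoperative change

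*Combined protocol and SAP*

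**What the plan says.** Section 3.0 gives as the second specific aim "To estimate the effect size of a multimodal prehabilitation program for important postoperative outcomes", and lists functional capacity and physical function, anxiety and depression, and quality of life. It expects Cohen's effect sizes of about 1.6 for functional capacity and 0.4 for quality of life.

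Section 13.0 gives the estimator: "Effect size will be estimated by comparing physical function before and after the prehabilitation intervention", "as measured by the 5RSTS and the 2-minute step tests", expressed as Cohen's d. SF-36 and HADS are given no d; their changes "before surgery and at the 6-week and 24-week study periods following surgery will be calculated".

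The design has one arm. Section 8.2 says "Eligible veterans who consent will enroll in a program of individualized exercise training combined with nutritional support", and no control group, randomisation or external comparator is described anywhere. Section 5.1 plans to "enroll a total of 24 patients over 2 years". Section 8.2.3 schedules the function tests at T1 (baseline), T2 (before surgery), T3 (discharge) and T4 (6 weeks after surgery).

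On use, Section 2.0 says "These findings are expected to inform the design of a larger multicenter trial", a trial whose stated targets are surgical outcomes and resource use.

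**The concern.** One of the two stated aims names a quantity that the analysis does not estimate. There are two mismatches.

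- **Timing.** The aim speaks of postoperative outcomes. A comparison before and after prehabilitation, on the T1 and T2 schedule, ends before the operation. T3 and T4 function results are collected but are not named in the effect-size analysis.
- **Attribution.** A change in a cohort where everyone is treated is not the effect of the treatment. The function change also contains regression to the mean, practice, any natural course while waiting for surgery, and selection of those who continue. The SF-36 and HADS changes at 6 and 24 weeks also contain the operation and recovery from it.

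Nothing in the documents labels the d as uncontrolled or limits how it may be read. At stake is what the final report may claim under Aim 2, and which numbers are handed to the larger trial.

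**Working it through.** **1. Aim against estimator**

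| | Aim 2 (Section 3.0) | Analysis (Section 13.0) |
|---|---|---|
| Quantity | Effect size of the program | Before-after change in treated patients |
| Time | Postoperative | T1 to T2, preoperative (function); across surgery (SF-36, HADS) |
| Measures with a d | Function, mood and quality of life implied | 5RSTS and step test only |
| Comparator | Needed | None |
| Standardiser of d | Not given | Not given |

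**2. The plan's own figures.** The expected 1.6 and 0.4 cannot be reproduced, because no mean change, SD or pre-post correlation is stated. The 24 patients rest on surgical volume and published participation and attrition, not on power, so nothing is inconsistent there.

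**3. What the observed change contains.** For function,

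mean(T2 − T1) = program + regression to the mean + practice + natural course + selection of continuers.

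The data supply the left-hand side only. Each other term has a source in the documents:
- regression to the mean: Section 5.2.1 admits patients on a slow 5RSTS and/or a low step-test score, and Section 8.1 makes that clinic test the baseline;
- practice: the same tests are repeated (Section 8.2.3), possibly in person once and remotely another time;
- natural course: surgery is at least 21 days away (Section 5.2.1);
- selection: anyone unable to continue is withdrawn, and research follow-up then stops (Section 12.0).

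There is one equation and five unknowns, and a larger N does not help.

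**4. Size of regression to the mean, with zero true change.** Reliability r is assumed to be 0.70 to 0.95. Table 1 calls 5RSTS reliability good to high but gives no figure.

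*Bounding case: entry on the step test at or below the 25th percentile only.* With a normal score, the mean of those selected is −0.3178/0.25 = −1.271 SD. The expected retest gain is (1 − r) × 1.271, which is 0.381 SD at r = 0.70 and 0.064 SD at r = 0.95. The SD among those selected is √(1 − 1.271 × (1.271 − 0.6745)) = 0.492. So d on the baseline SD is 0.381/0.492 = 0.78, down to 0.064/0.492 = 0.13.

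*Actual and/or rule.* This was simulated, assuming the two tests' true scores correlate 0.5 and the 11-second cut lies at the population mean:

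| r | d, step test | d, 5RSTS |
|---|---|---|
| 0.70 | 0.068 | 0.205 |
| 0.80 | 0.045 | 0.144 |
| 0.90 | 0.022 | 0.075 |
| 0.95 | 0.011 | 0.039 |

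Varying the correlation from 0.3 to 0.7 and using three positions of the 5RSTS cut gives 0.00 to 0.21 on the pooled SD, and 0.00 to 0.09 when reliability is 0.90 to 0.95. The top of the range is 0.21/1.6 = 13% of the d expected for functional capacity.

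**5. The standardiser matters.** If d is divided by the SD of change (d_z), the equivalent on the between-patient SD is d_z × √(2(1 − r′)), where r′ is the T1-T2 correlation. A d_z of 1.6 is then 1.60, 1.24, 1.01 or 0.72 for an assumed r′ of 0.5, 0.7, 0.8 or 0.9.

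**6. Precision.** With 24 complete pairs and an observed d_z of 1.6, t = 1.6 × √24 = 7.84 on 23 degrees of freedom. The noncentral-t 95% interval is 0.98 to 2.20. Section 13.0 asks for no interval.

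**The case against.** The strongest reply is that this is a pilot and says so. Section 3.0 calls the work exploratory, and its central hypothesis concerns feasibility and safety. Section 4.2 leaves effectiveness to future, adequately powered trials. Section 13.0 says openly that the comparison is before and after, and describes SF-36 and HADS only as changes. A within-patient change is a legitimate thing for a pilot to report.

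All of that stands, and it is good reason not to ask for a control arm. It does not turn a before-after change into the effect size of the program for postoperative outcomes, which is what Aim 2 promises.

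A reader might infer more than the documents support:
- *That the d must overstate benefit.* Practice and regression to the mean would push it up, but function may decline while patients wait for high-risk surgery. The documents give no untreated course, so the sign of the net bias is open.
- *That the next trial will be too small.* Section 2.0 says only that the findings will inform its design. Nothing says this d will set its sample size, and a d on 5RSTS is not the effect size for surgical outcomes or resource use.
- *That regression to the mean could produce the 0.4 expected for quality of life.* SF-36 is not an entry test, so the calculation above does not apply to it.
- *That a postoperative d could show spurious harm.* Section 13.0 specifies no d for SF-36 or HADS.

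**Conclusion.** The point holds as one of labelling and interpretation. Aim 2 names the program's effect size for postoperative outcomes; the plan yields an uncontrolled preoperative change in two function tests, and uncontrolled changes in questionnaires across surgery. That follows from the text alone and needs no assumption.

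The size of the discrepancy cannot be given, because most of its components are unknown. The one component worked out here, regression to the mean under the and/or rule, is a d of about 0.00 to 0.21. That rests on normal scores and on assumed reliability, correlation between tests and position of the 5RSTS cut. It could not by itself account for 1.6. The scale of d is also undefined until a standardiser is named.

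**What to change.** In Sections 3.0 and 13.0, with matching wording in Section 5.3:

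1. Restate the aim and the analysis as estimating within-participant change: T1 to T2 for function before surgery, baseline to T4 for function after surgery, and baseline to T4 and T5 for SF-36 and HADS.
2. Name the standardiser for d (baseline SD, pooled SD or SD of change). Report the raw mean change and d with 95% confidence intervals, and the number of patients contributing to each.
3. Add a sentence that these are uncontrolled changes and not the between-group effect of the program.
4. List what the pilot can pass to the larger trial: SDs, the T1-T2 correlation, attrition and compliance.
5. Reconcile the SF-36 schedule, which runs T1 to T5 in Section 8.2.3 but only T1, T4 and T5 in Table 1, so that its baseline is unambiguous.

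No arm, patient, visit or test is added. The cost is an amendment to the wording, a few more lines of analysis, and a stated deliverable that is less ambitious.

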## **4.0 Risk/Benefit Assessment**

### **4.1 Risk Assessment**

There are minimal risks associated with the proposed prehabilitation program. Generally, nutrition and exercise are known to improve health. Physical injury or discomfort are potential risks and are inherent in any exercise, rehabilitation or prehabilitation program. Patients invited to participate will be screened by qualified physical therapists as part of the screening evaluation and the inability to complete the physical functional assessment will be cause for exclusion. Also, patients for whom physical activity is inappropriate or cognitive impairment affects their ability to consent for participation or to successfully participate in the exercise program will not be enrolled. The team has extensive experience with tele-exercise therapies, including strategies for optimizing safety during individual, independent, home-based exercise. Examples of home-based exercises include marching in place, standing (potentially supported) while tapping a heel or toes, performing chair stands, and moving a leg or arm against a resistance band. It is entirely self-regulated, and any advancement will be based on self-reported levels of exertion.

Similarly, the nutrition and vitamin supplementation will be closely monitored by nutrition experts and adjusted based on personal telephone check-ins. Patients with advanced kidney disease are excluded from the study and those with renal impairment (KDIGO 3a and 3b) will receive reduced protein supplement in accord with ESPEN and 2012 KDIGO Guidelines. Renal function will be regularly monitored to ensure there is no adverse effect from the nutritional intervention.

Participation in our study poses no additional cost and every effort will be made to preserve the privacy and confidentiality of participants.

The similarity of the study interventions to conditions potentially encountered in daily life coupled with the measures taken to protect participants from adverse impact create a total risk that is minimal. The types of exercise resemble activities of daily living, especially in that they are self-regulated, and no patient will, or could be forced to do something they choose not to do.

### **4.2 Benefit Assessment**

The benefit of participation in this study is available to both current enrollees and future patients. If a monitored prehabilitation program paired with nutrition support is found to be feasible, acceptable, and safe, and in the future, adequately powered clinical trials found to be effective, significant improvement to perioperative care is possible. Furthermore, the telehealth component of this program would facilitate delivery of prehabilitation to rural populations and those with limited support or access to transportation.

